13.2 Pharmacokinetic parameter calculations

Pharmacokinetic parameters will be calculated by the sponsor based on non-compartmental methods using Phoenix 64 (version 8.1 or later). The following parameters will be derived for each subject for the Cycle 1 and Cycle 2 profiles:

AUC _{0-last}	Area under the plasma concentration-time curve, from time zero to the last quantifiable concentration (mass x time x volume ⁻¹)
AUC _{0-7days}	Area under the plasma concentration time curve, from time

	zero to seven days (mass x time x volume ⁻¹)
AUC _{inf}	Area under the plasma concentration time curve from time zero to infinity (mass x time x volume ⁻¹)
C _{max}	Maximum observed drug concentration in plasma after each administration (mass x volume ⁻¹)
t _{max}	Time of maximum observed concentration (time)
t _{1/2}	The elimination half-life associated with the terminal slope (λz) of a semi logarithmic concentration-time curve (time)
CL	Apparent total plasma clearance (volume x time ⁻¹)

Elimination half-life t_{1/2} and associated parameters (AUC_{inf} and CL) will be reported only for cases where a sufficient number of observations above the lower limit of quantification (LLOQ) are available in the linear elimination phase. The AUC_{0-7days} will be calculated only if the plasma concentration after 7 days (the Day 8 predose sample) has a quantifiable result or if t_{1/2} can be calculated. Additional parameters – such as dose normalized C_{max} and AUCs, apparent volume of distribution, accumulation ratios between the Cycle 2 and Cycle 1 exposures – may be calculated to fully characterize the PK profiles of GEN3009.

All pharmacokinetic parameters for each profile (Cycle 1 and Cycle 2) will be listed by subject and summarized by dose level and by ADA status. All subjects in the PK dataset for which PK parameters could be calculated will be included in the descriptive statistics for those parameters. Descriptive statistics provided will include the number of subjects, arithmetic mean, standard deviation (SD), arithmetic coefficient of variation, reported as a percentage (CV%), median, minimum and maximum. Geometric mean and geometric CV% will be calculated for continuous PK parameters. T_{max} will be presented as median, minimum and maximum.

If deemed applicable, compartmental modelling approaches may also be applied.

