A high degree of receptor occupancy (ie, target saturation) throughout the dosing interval is often correlated with optimal anti-tumor activity of therapeutic antibodies with similar MoAs (CDC, ADCC, ADCP [eg, daratumumab and ofatumumab], etc). Therefore, maintaining a high % of CD37 saturation would be critical for efficacy. IgG1 Fc-domain associated effector functions including CDC, ADCC, and ADCP are known to require a high degree of receptor occupancy throughout the dosing interval for optimal effect. In cynomolgus monkey, approximately linear PK was observed at 3 mg/kg and above, suggesting sustained saturation of target mediated clearance. A near complete depletion of B cells in circulation was observed at these dose levels. In patients, the additional CD37 on malignant cells is expected to increase the dose required for sustained target saturation compared to healthy cynomolgus monkeys. Target mediated clearance is expected to be reduced over the course of treatment at efficacious dose levels due to the depletion of malignant cells, so that target saturation can be maintained with less frequent dosing. The schedule therefore starts with weekly dosing for the first 3 cycles of 28 days before the dosing frequency is reduced to once every 2 weeks (six 28-day cycles; Cycle 4 through 9) and once every 4 weeks (Cycle 10 and onwards).

Preliminary results from the Dose Escalation part of GCT3009-01 among patients treated with GEN3009 at doses ranging from █ mg to █ CCI mg at dose intervals of weekly in cycles 1-3, biweekly in cycles 4-9, and monthly from cycle 10 and beyond have shown the following:

- GEN3009 was well-tolerated with clinically manageable side effects at doses up to █ CCI mg. The most common TEAEs were IRRs and the most frequent laboratory

abnormalities were neutropenia. Both IRR and neutropenia are not dose-dependent; No dose-dependent toxicity has been observed so far.

- From the PK perspective, GEN3009 exhibited target-mediated drug disposition as expected, particularly at lower dose/concentration levels and resulting in rapid clearance of the drug-CD37 complex. High interindividual variability in target-mediated clearance was observed. For the majority of subjects doses up to **CCI** mg and for one out of three subjects at **CCI** mg were not sufficient to maintain saturating exposure throughout the dosing interval.

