6.4 Dosage(s) and Administration

6.4.1 GEN3009 Monotherapy Cohorts

GEN3009 will be administered as an IV infusion according to the following schedule until 1 or more of the discontinuation criteria in Section 8.1 are met:

- Cycles 1 through 3: Days 1*, 8, 15, and 22 (once weekly for a 28-day cycle)
- Cycles 4 through 9: Days 1 and 15 (every 2 weeks for a 28-day cycle)
- Cycle 10 and beyond: Day 1 (every 4 weeks for a 28-day cycle)

*At dose levels \geq CCI mg, the first dose of GEN3009 can be split into 2 consecutive days (eg, CCI mg at C1D1 and remaining amount at C1D2) after approval of the sponsor's medical monitor.

Refer to the GEN3009 investigational medicinal product (IMP) manual for additional information and guidance on dosage and administration.

Refer to Section 6.6 for information regarding concomitant therapy. Detailed dose modification guidance is provided in Section 7.

In the Dose Escalation, the DLs will be determined by the starting dose and the escalation steps taken in the trial (refer to Section 4.1.1).

During the Dose Escalation, all subjects must remain at the clinic for at least 4 hours after each GEN3009 administration in Cycle 1. Subjects must be instructed to contact the investigator should signs or symptoms of IRRs occur following discharge from the 4-hour observation period. An

observation of up to 24 hours postdose during Cycle 1 is permissible at the discretion of the investigator.

During the Expansion (including safety run-in), all subjects are required to remain at the clinic for at least 2 hours after the GEN3009 administration in Cycle 1. Subjects must be instructed to contact the investigator should signs or symptoms of IRRs and/or CRS (eg, fever, lightheadedness, shortness of breath, etc) occur following discharge.

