11.6 Pharmacokinetics

Individual curves of plasma concentration of GEN3009 or GEN3013 versus time after end of infusion will be presented for all subjects, including information on actual administered dose. All available data will be shown in these figures. Concentrations below the limit of quantification will be marked separately.

PK parameters ([Table 33](#)) will be calculated based on non-compartmental methods and will be calculated separately for Cycle 1 and Cycle 2. Elimination half-life ($T_{1/2}$) and parameters based on $T_{1/2}$ (area under the curve [$AUC]_{inf}$, CL) will be calculated only if a sufficient number of observations are available above LLOQ.

The relation between derived PK parameters and covariates such as actual dose, weight and dose, and selected laboratory parameters will be evaluated graphically.

If deemed applicable compartmental modeling approaches to parameter estimation will be applied.

Descriptive statistics of PK endpoints will include arithmetic and geometric means, standard deviations, CV%, median, minimum and maximum.

Further exploratory analyses of PK data may be performed.

Table 33 Non-compartmental Pharmacokinetic Parameters

$AUC_{0-7\text{days}}$	The AUC from time zero to Day 7 (mass \times time \times volume $^{-1}$)
AUC_{inf^a}	The AUC from time zero to infinity (mass \times time \times volume $^{-1}$)
AUC_{last}	The AUC from time zero to last quantifiable measurement (mass \times time \times volume $^{-1}$)
C_{max}	The maximum (peak) observed plasma, blood, serum, or other body fluid drug concentration after single dose administration (mass \times volume $^{-1}$)
T_{max}	The time to reach maximum (peak) plasma, blood, serum, or other body fluid drug concentration after single dose administration (time)
C_{trough}	Observed concentration at the end of the dosing interval (mass \times volume $^{-1}$)
$T_{1/2}^a$	The elimination half-life associated with the terminal slope (λz) of a semi logarithmic concentration-time curve (time)
CL^a	The total body clearance of drug from the plasma (volume \times time $^{-1}$)

^a Calculated only if feasible.

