3.5 Treatment administration schedule

The Dose Escalation part of the trial will consist of approximately 7 dose level cohorts of subjects and additional intermediate dose levels may be explored based on emerging data, as described in protocol 4.1.1. The Dose Expansion part of the trial will include 3 diagnosis cohorts of subjects, with parallel enrolment, who will be treated with the RP2D as determined in the Dose Escalation part of the trial.

GEN3009 will be administered intravenously in 28 day cycles, as per Section 4.1 of the protocol:

- Cycles 1, 2, and 3: Administered on Days 1, 8, 15, and 22 (once weekly)
- Cycles 4, 5, 6, 7, 8, and 9: Administered on Days 1 and 15 (every 2 weeks)

- Cycles 10 and later: Administered on Day 1 (every 4 weeks)

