12.2 Protein Expression

CCI

13 Pharmacokinetic (PK) Analyses

Venous blood samples are collected prior to GEN3009 dosing, and specified time points after dosing, as described in Table 1-3 (Dose Escalation), Table 1-6 (Dose Expansion) and Section 9.5 of the protocol, for the measurement of plasma concentrations of GEN3009. Samples will also be collected at the End of Treatment visit.

The concentration of GEN3009 in plasma samples will be determined by a validated, specific, and sensitive ligand binding assay, at the assay CRO.

13.1 *The PK analysis and output to be generated are detailed in the next paragraphs. In short, GEN3009 concentration data will be presented graphically and summarized by dose group and ADA status. The sponsor will calculate PK parameters based on non-compartmental methods and will provide the results to be included in the Tables, Listings and Figures as part of this SAP. Graphical exploration of the relationships between exposure and covariates, observations of safety, efficacy or pharmacodynamic biomarkers will be performed by the sponsor outside of the scope of this SAP. GEN3009 Concentration data*

Individual observations of plasma concentration will be listed chronologically for each subject. Concentrations below the lower limit of quantification (LLOQ) will be reported as <LLOQ in data listings and omitted from summary statistics and graphs.

GEN3009 concentration data will be presented graphically, using individual curves of concentrations. All available data will be shown in these figures. Separate figures will be presented showing the plasma concentration-time profiles after the first dose of Cycle 1 and Cycle 2.

Concentrations will be summarized using both arithmetic and geometric means, standard deviations, coefficient of variations expressed as percentages (CV%), medians, minimums and maximums. Summaries will be presented overall and by ADA status, as described in Section 11.8.

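### AUCinf and clearance of GEN3009 are also derived from the Cycle 2 profile, which follows four earlier weekly doses, so Cycle 2 clearance is biased low wherever drug persists for a week

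*SAP*

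**What the plan says.** SAP section 13.2 gives a single list of non-compartmental parameters and states: "The following parameters will be derived for each subject for the Cycle 1 and Cycle 2 profiles". The list includes AUCinf, defined as "Area under the plasma concentration time curve from time zero to infinity", the elimination half-life, and CL, defined as "Apparent total plasma clearance". All parameters are to be listed and summarised for each profile. Half-life, AUCinf and CL are grouped together and reported only when enough quantifiable observations are available in the elimination phase. That is the only reporting condition. Accumulation ratios between the two cycles appear as optional extras.

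Protocol section 11.6 agrees: the parameters in Table 33 "will be calculated separately for Cycle 1 and Cycle 2", and AUCinf and CL are described as depending on half-life.

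SAP section 13.1 shows which dose starts each profile: "Separate figures will be presented showing the plasma concentration-time profiles after the first dose of Cycle 1 and Cycle 2". Under SAP section 3.5 and protocol section 6.4.1, GEN3009 is given on Days 1, 8, 15 and 22 of Cycles 1 to 3.

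Neither document writes a formula for CL, gives a carry-over rule, corrects for the predose concentration, or defines a clearance based on the dosing interval.

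**The concern.** Dividing one dose by AUCinf gives clearance only if all the drug under the curve came from that dose. This is true of the first Cycle 1 dose. It is not true of Cycle 2 Day 1, when drug from four weekly doses may still be in the body.

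The direction of the error makes it easy to misread. Protocol section 4.3.1 states that "Target mediated clearance is expected to be reduced over the course of treatment at efficacious dose levels due to the depletion of malignant cells", and gives this as the reason for less frequent dosing after Cycle 3. Section 4.3.2 uses the same reasoning for the sparser combination schedule. A Cycle 2 CL that is low only because of carry-over would look like confirmation of that expectation.

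**Working it through.** The documents state no half-life and no clearance, so there is no figure of theirs to reproduce. The check asks what dose/AUCinf returns after the fifth weekly dose when true clearance has not changed.

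**Inputs**
- Doses before Cycle 2 Day 1: four (Cycle 1 Days 1, 8, 15 and 22), from SAP 3.5 and protocol 6.4.1.
- Dosing interval: 7 days, from the same sections.
- CL = dose/AUCinf: implied by SAP 13.2 and protocol 11.6, not written.
- Half-life: assumed, 1 to 21 days.

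**Direction.** By mass balance, the drug eliminated after Cycle 2 Day 1 is that dose plus the amount A still in the body beforehand. Dose/AUCinf therefore equals average clearance multiplied by dose/(dose + A). This is below 1 whenever A is above zero, and the argument does not need linear kinetics.

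**Size, one compartment with constant clearance.** Let r = 2^(-7/half-life), the fraction of a dose left after one week.
- AUCinf after dose 5 divided by AUCinf after dose 1: S = 1 + r + r² + r³ + r⁴.
- Apparent CL divided by true CL: 1/S.
- Example at 7 days: r = 0.5, S = 1 + 0.5 + 0.25 + 0.125 + 0.0625 = 1.9375, and 1/S = 0.516.

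The last column shows the alternative dose/AUC0-7days, whose ratio to true CL is 1/(1 - r⁵).

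| Half-life (days) | r | S | Dose/AUCinf vs true CL | Dose/AUC0-7days vs true CL |
|---|---|---|---|---|
| 1 | 0.008 | 1.008 | 0.99 | 1.00 |
| 3.5 | 0.250 | 1.332 | 0.75 | 1.00 |
| 7 | 0.500 | 1.938 | 0.52 | 1.03 |
| 14 | 0.707 | 2.811 | 0.36 | 1.22 |
| 21 | 0.794 | 3.321 | 0.30 | 1.46 |

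**Check at the planned sampling times.** A numerical non-compartmental analysis used the dose-escalation times in protocol Table 4 (predose, end of infusion, +2, +4, +24 and +72 hours, Day 8 predose) and an assumed 3-hour infusion. At half-lives of 1, 3, 7, 14 and 21 days it agreed with the formula within 0.002.

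**Two compartments (illustrative).** Assumed values, in litres and days: central volume 3, peripheral volume 2.5, intercompartmental clearance 0.5, and clearance 1.5, 0.6, 0.3 or 0.2. Terminal half-lives were 5.1, 8.4, 14.5 and 20.8 days, and the Cycle 2/Cycle 1 CL ratios were 0.82, 0.54, 0.34 and 0.26. In these runs Cycle 1 CL was itself too high (1.08 to 1.99 times the true value), because one week of sampling is short for the terminal phase.

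**Where CL could be reported.** Table 4 (dose escalation) and Table 12 (combination) have serial GEN3009 samples after Cycle 2 Day 1. Table 7 (monotherapy expansion) appears to have only predose, end of infusion and the Day 8 predose, so the SAP's sufficiency condition would seldom be met there.

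**The case against.** The strongest reply is that the harm is limited, and much of it stands.

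- **The formula is inferred.** If the sponsor means dose over the weekly AUC for Cycle 2, the spurious fall does not arise. But both documents tie CL to half-life and AUCinf, and neither mentions an interval-based clearance. Cycle 2 AUCinf would be inflated in any case.
- **Carry-over may be absent.** Protocol section 4.3.1 reports rapid target-mediated clearance at lower doses and wide variation between subjects. Where nothing remains after a week there is no bias, so a reader should not infer that clearance will appear to fall in every subject or at every dose. However, the higher doses added to dose escalation are meant to keep exposure saturating through the interval, which is the setting where drug persists.
- **No decision is shown to use Cycle 2 CL.** A reader might infer that dose or schedule choices rest on a planned comparison of clearance between cycles. The documents do not support that. Parameters are summarised profile by profile, and the only cross-cycle quantity is an optional ratio of exposures. Protocol section 4.1.1.1 guides the RP2D by the totality of data and PK/pharmacodynamic modelling. The schedules are already set, on an expectation.
- **GEN3013.** It is tempting to carry the same percentages over to GEN3013. SAP 13.2 covers GEN3009 only, and GEN3013 is given subcutaneously, so absorption matters. Its first dose is the 0.16 mg priming dose on Day 8, and Table 12 shows no GEN3013 sample after it until the Day 15 predose. No GEN3013 figure is offered here.

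**Conclusion.** The point holds for GEN3009. As written, the plan produces a Cycle 2 AUCinf that is too high and a Cycle 2 CL that is too low wherever drug is measurable before the Cycle 2 Day 1 dose. The direction follows from mass balance, given CL = dose/AUCinf. The size rests on an assumed half-life, linear one-compartment kinetics and constant clearance: about 1% low at 1 day, 25% at 3.5 days, 48% at 7 days and 64% at 14 days. The bias is negligible at low doses that clear within the week.

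It mainly affects dose escalation and the combination cohort. The practical risk is one of interpretation: an uncorrected Cycle 2 CL should not be read as evidence that target-mediated clearance has fallen.

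**What to change.** In SAP 13.2, and in protocol 11.6 with Table 33:

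1. Limit AUCinf and dose/AUCinf clearance for GEN3009 to the first-dose Cycle 1 profile.
2. For Cycle 2, report AUC0-7days, Cmax, Ctrough and the accumulation ratio. Ctrough is in Table 33 but not in the SAP list, and the accumulation ratio is now optional, so both need adding. The SAP abbreviation list marks AUC0-7days as applying to Cycle 1 Day 1 only, whereas 13.2 derives it for both cycles. These should be reconciled.
3. Take any Cycle 2 clearance from the compartmental or population modelling that both plans already allow. Dose/AUC0-7days is acceptable only near steady state, since it overstates clearance by about 22% at a 14-day half-life and 46% at 21 days. Subtracting the predose concentration divided by the terminal slope is not a safe general correction: it is exact only when the residual drug declines log-linearly, which target-mediated clearance does not guarantee.
4. State that an uncorrected Cycle 2 CL is not to be used as evidence of reduced target-mediated clearance.

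The cost is wording. No new samples are needed. The SAP is based on protocol version 4.0 and the current protocol is Amendment 5, so the change can be made when the SAP is brought up to date.

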- d. On dosing days, vital signs are performed predose and postdose, and more frequently at the discretion of the investigator. If the subject has stable vital signs and no other issues, the subject may be discharged from the clinic after all assessments are completed as required by protocol. Subjects must be instructed to contact the investigator should signs or symptoms of infusion-related reactions occur following discharge from the clinic.
- e. In triplicate, 5 minutes apart (\pm 5 minutes), before GEN3009 administration and 1-2 hours (\pm 15 minutes) after administration. During Cycle 4 and for all subsequent cycles, ECGs are required at predose only. During an unscheduled visit, ECG is performed only if clinically indicated.
- f. All AEs must be reported from the first GEN3009 dose until 30 days after the last dose. If the subject initiates new anti-lymphoma therapy within 30 days of the last dose of GEN3009, the safety follow-up visit should be performed prior to starting new anti-cancer therapy.

- g. Refer to Section [9.2.2.1](#) for imaging requirements.
- h. Only for subjects with positive serology.

Table 7 Visit Assessment Schedule for PK and ADA– Expansion GEN3009 Monotherapy

Treatment Cycle: 28-day cycle	Section	Cycle 1								
		1d	2d	4d	8d	9d	15d	16d	22d	23d
Day	9.5, 9.6	ADA/PK	PK ^c		PK		PK		PK	
Visit window		PK	PK ^c		PK		PK		PK	
Predose (-30 minutes)		PK ^b	PK ^c							
End of infusion ^a (+5 minutes)			PK ^b							
End of infusion +2 hours (+1 hour)				PK						
End of infusion +24 hours (±2 hours)										
End of infusion +72 hours (±24 hours) ^d										

Treatment Cycle: 28-day cycle	Section	Cycles 2 and 3				Cycles 4-9		Cycle 10 and Beyond	Unscheduled	Treatment Discontinuation Visit
		1d	8d	15d	22d	1d	15d			
Day	9.5, 9.6	1d	+2d	+2d	+2d	+3d	±3d	±4d		
Visit Window		ADA ^e / PK	PK	PK	PK	ADA ^e / PK	PK	ADA ^e / PK		
Predose (-30 min)		PK								
End of infusion ^a (+5 min)										
Unscheduled Visit									ADA/ PK	ADA/ PK

Note: Sample collection timing may be modified during the trial based on emerging data.

- a. After flush.
- b. Only in case of full infusion on Day 1.
- c. Only in case of split dose between Day 1 and Day 2.
- d. In case of split dose between Day 1 and Day 2, the Day 4 sample will be 48 hours after the complete infusion.
- e. Even cycles only.

Table 8 Visit Assessment Schedule for Biomarkers – Expansion GEN3009 Monotherapy

Treatment Cycle: 28-day cycle	Section	Cycles 1 and 2								

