- e. In triplicate, 5 minutes apart (\pm 5 minutes), before GEN3009 administration and 1-2 hours (\pm 15 minutes) after administration. During Cycle 4 and for all subsequent cycles, ECGs are required at predose only. During an unscheduled visit, ECG is performed only if clinically indicated.
- f. All AEs must be reported from the first GEN3009 dose until 60 days after the last dose. If the subject initiates new anti-lymphoma therapy within 60 days of the last dose of GEN3009 and/or GEN3013, the safety follow-up visit should be performed prior to starting new anti-cancer therapy.
- g. After completion of Cycle 12, subjects who are in SD or better will have the option to continue receiving GEN3013 every 4 weeks until any discontinuation criteria is met.
- h. Refer to Section [9.2.2.1](#) for imaging requirements.
- i. Only for subjects with positive serology.
- j. Even cycles only.

Table 12 Visit Assessment Schedule for PK and ADA – Expansion GEN3009 + GEN3013 (including Safety Run-in)

Treatment Cycle: 28-day cycle	Section	Cycle 1									
		1d	2d	4d	8d	9d	15d	16d	18d	22d	23d
Predose (-30 min)	9.5, 9.6	ADA: 09 and 013 / PK: 09 only	PK: 09 only ^c		PK: 09 and 13		PK: 09 and 13			PK: 09 and 13	
Start of GEN3013 Injection +1 hour (+15 min)							PK: 13 only			PK: 13 only	
End of GEN3009 infusion ^a (+5 min)		PK: 09 only	PK: 09 only ^c		PK: 09 only		PK: 09 and 13			PK: 09 and 13	
End of GEN3009 infusion +2 hours (+1 hour)		PK: 09 only ^b	PK: 09 only ^c								
End of GEN3009 Infusion +24 hours (\pm 2 hours)			PK: 09 only ^b					PK: 13 only			PK: 13 only
End of GEN3009 Infusion +72 hours (\pm 24 hours) ^d				PK: 09 only					PK: 13 only		

Treatment Cycle: 28-day cycle	Section	Cycle 2									
		1d	2d	4d	8d	9d	15d	16d	22d	23d	
Predose (-30 min)	9.5, 9.6	ADA/PK: 09 and 13			PK: 09 and 13		PK: 09 and 13		PK: 09 and 13		
Start of GEN3013 injection +1 hour (+15 min)		PK: 13 only									
End of GEN3009 infusion +5 min ^a (+5 min)		PK: 09 and 13									
End of GEN3009 infusion +2 hours (+1 hour)		PK: 09 only									
End of GEN3009 Infusion +24 hours (\pm 6 hours)			PK: 09 and 13								
End of GEN3009 Infusion +72 hours (\pm 24 hours)				PK: 09 and 13							

Treatment Cycle: 28-day cycle	Section	Cycle 3	Cycle 4-12	Cycle 13 and Beyond	Unscheduled	Treatment Discontinuation Visit
----------------------------------	---------	---------	------------	---------------------	-------------	---------------------------------

Day		1d	8d	15d	22d	1d	1d		

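### In monotherapy Expansion, Cycle 2 AUC rests on two post-dose samples against five in Cycle 1, so Cycle 2 AUC0-7days and any Cycle 2/Cycle 1 AUC ratio carry a sampling artefact

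*SAP*

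**What the plan says.** SAP 13.2 lists AUC0-last, AUC0-7days, AUCinf, Cmax, tmax, t1/2 and CL, introduced by: "The following parameters will be derived for each subject for the Cycle 1 and Cycle 2 profiles". Conditions follow. For half-life, AUCinf and CL, the SAP says that values "will be reported only for cases where a sufficient number of observations above the lower limit of quantification (LLOQ) are available"; these observations must fall on the linear part of the decline. AUC0-7days is calculated "if the plasma concentration after 7 days (the Day 8 predose sample) has a quantifiable result", or if a half-life can be obtained. AUC0-last has no condition. Optional extras include "accumulation ratios between the Cycle 2 and Cycle 1 exposures". Compartmental modelling is optional in 13.2, and population modelling in 13.3.

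Protocol 11.6 also plans non-compartmental parameters separately for Cycle 1 and Cycle 2, with no exception for any part of the trial. Its Table 33 marks AUCinf, T1/2 and CL as dependent on feasibility. Protocol Table 18 makes CL, AUC7days, AUClast, Cmax, Tmax, Ctrough and T1/2 secondary endpoints of monotherapy Expansion. Ctrough is absent from the SAP 13.2 list.

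The sampling schedule is protocol Table 7, "Visit Assessment Schedule for PK and ADA– Expansion GEN3009 Monotherapy".

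**The concern.** The analysis text treats the two cycles alike, but the sampling does not. In monotherapy Expansion (three cohorts of 20) the post-infusion samples at 2, 24 and 72 hours exist in Cycle 1 and disappear in Cycle 2. A Cycle 2 AUC0-7days can still pass the SAP's test and would be listed beside a Cycle 1 value built on a much fuller profile. Any ratio of the two then mixes a change in exposure with a change in sampling density, which could mimic or hide a real change. AUC7days and AUClast are named secondary endpoints, and protocol 4.3.1 reports target-mediated disposition, so a straight-line decline on the log scale cannot be taken for granted.

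**Working it through.** **Step 1: count samples describing the Day 1 dose (unsplit dose, GEN3009).**

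| Part and cycle | Source | Post-dose samples |
|---|---|---|
| Monotherapy Expansion, Cycle 1 | Table 7 | end of infusion, +2 h, +24 h, +72 h, Day 8 predose: 5 |
| Monotherapy Expansion, Cycle 2 | Table 7 | end of infusion, Day 8 predose: 2 |
| Dose Escalation, Cycle 2 | Table 4 | same serial schedule as Cycle 1 |
| Combination cohort, Cycle 2 | Table 12 | end of infusion, +2 h, +24 h, +72 h, Day 8 predose: 5 |

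The Table 7 block for Cycles 2 and 3 has no timed row later than end of infusion. Day 15 and Day 22 predose samples are also drawn, but they follow later weekly doses. Table 12 keeps rows such as "End of GEN3009 Infusion +24 hours" in Cycle 2. Only monotherapy Expansion is affected.

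**Step 2: apply the SAP conditions.** A quantifiable Day 8 predose value releases AUC0-7days, with nothing required between end of infusion and Day 8. If that value is below the quantification limit, Cycle 2 AUC0-last stops at end of infusion while Cycle 1 can run to +72 h, so the two are not comparable. Two points fix a line exactly and the first is the peak, so no terminal slope can be properly estimated.

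**Step 3: size.** There is no figure in the plan to reproduce. Assumed: bi-exponential decline, fast fraction f 30–50%, fast half-life 12–36 h, slow half-life 3–14 days, instantaneous dosing. Cycle 2 Day 1 is the fifth weekly dose, so n = 1 for Cycle 1 and n = 5 for Cycle 2:

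C(t) = Σ over j = 0 to n−1 of [f·exp(−kf(t+168j)) + (1−f)·exp(−ks(t+168j))], with k = ln 2 / half-life.

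True AUC0-168 = f(1−exp(−168n·kf))/kf + (1−f)(1−exp(−168n·ks))/ks.

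Worked case, f = 0.4, half-lives 24 h and 7 days (kf = 0.02888, ks = 0.004126 per hour):

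- True Cycle 1 AUC: 13.74 + 72.71 = 86.45. True Cycle 2 AUC: 13.85 + 140.88 = 154.73. True ratio: 154.73/86.45 = 1.79.
- Cycle 1 concentrations at 0, 2, 24, 72, 168 h: 1.000, 0.973, 0.743, 0.496, 0.303. Linear trapezoid: 1.97 + 18.88 + 29.74 + 38.35 = 88.94 (+2.9%).
- Cycle 2 concentrations at 0 and 168 h: 1.566 and 0.584. Linear: 168 × (1.566 + 0.584)/2 = 180.6 (+16.7%). Log: 168 × (1.566 − 0.584)/ln(1.566/0.584) = 167.3 (+8.1%).
- Reported ratio, linear: 180.6/88.94 = 2.03 against 1.79 (+13.5%). With the log rule Cycle 1 is 87.67, giving 167.3/87.67 = 1.91 (+6.6%).

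Over the whole assumed grid:

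| | Linear rule | Log rule |
|---|---|---|
| Cycle 2 AUC0-7days error | 5–73% high (median 17%) | 3–26% high (median 7%) |
| Cycle 2/Cycle 1 ratio error | 3–62% high | 2–23% high |

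**Step 4: other disposition models.** A separate simulation used one- and two-compartment models, with and without saturable elimination, and infusions of 2 or 6 h (central volume 3 L and CL 0.12–0.96 L/day, all assumed). Cycle 2 AUC0-7days error was +2% to +50% with the linear rule and −28% to +18% with linear-up/log-down. Ratio error ran from −24% to +40%. With strong saturable clearance and the log-down rule, a true ratio of 1.23 was reported as 0.94. The error was zero for mono-exponential decline with the log rule.

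**Step 5: is it the sampling?** In the same simulation, giving Cycle 2 the Cycle 1 times brought Cycle 2 AUC error to about −6% to +6%, and the ratio to within about 5% of truth.

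**The case against.** Much can be said for the plan. Half-life, AUCinf and CL are not reported for every subject: the SAP requires enough observations in the elimination phase and protocol Table 33 requires feasibility. A reader might take the opening sentence of SAP 13.2 to mean distorted half-lives and clearances throughout. The conditions that follow do not support that, although a sufficient number is left undefined.

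The ratio is optional. A reader might infer that it is the evidence for less frequent dosing. No passage says so: protocol 4.3.1 states falling target-mediated clearance as an expectation when explaining a fixed schedule, and draws its human PK conclusions from Dose Escalation, which has serial Cycle 2 sampling.

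A reader might also size the error from a single dose. On the same grid that gives 11–84% with the linear rule, but it overstates the problem because Cycle 2 Day 1 is the fifth weekly dose and part of the Cycle 1 error cancels in the ratio.

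The SAP abbreviation list glosses AUC0-7days as Cycle 1 Day 1 only, which may show an intention to leave Cycle 2 out. That conflicts with the operative text of 13.2, leaves AUC0-last untouched, and would needlessly drop Dose Escalation. Finally, the SAP is written to protocol version 4.0, whose sampling table is not available here. Whether it mismatched its own schedule is unknown, but current protocol 11.6 and Table 7 show the same conflict.

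All of this narrows the point. None of it removes the AUC0-7days and AUC0-last problem.

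**Conclusion.** The point holds for AUC0-7days and AUC0-last in Cycle 2 of monotherapy Expansion, and for any AUC ratio built on them. That the stated rule yields a one-segment AUC follows from the documents alone. The size does not: it depends on an unstated trapezoid rule and on unknown human disposition, and ranges from nothing to overstatement by more than half, with understatement of about a quarter possible under saturable elimination. The endpoint is secondary and descriptive, with no hypothesis test, and the primary response analysis is untouched. It should be corrected before the Expansion PK tables are produced.

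**What to change.** In SAP 13.2, aligned in protocol 11.6:

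- For monotherapy Expansion Cycle 2, report by non-compartmental methods only the observed end-of-infusion concentration (Cmax) and Ctrough. Add Ctrough to the SAP list, since it is already a protocol endpoint.
- Take any Cycle 2 AUC for this part from the compartmental or population modelling already allowed.
- Report Cycle 2/Cycle 1 AUC ratios only where both cycles have serial sampling: Dose Escalation and, for GEN3009, the combination cohort.
- Name the trapezoid rule and the minimum number of points for an AUC and for a terminal slope, and reconcile the abbreviation list with 13.2.

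The cost is wording in two documents, with no new samples. The downside is that some Cycle 2 AUC cells in monotherapy Expansion become not calculated. Adding post-infusion samples in Cycle 2 would also solve it, at the price of extra draws and visits.
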